For subjects enrolled in this pilot study, the mean change from Baseline to study Endpoint in the Aberrant Behavior Checklist (ABC) Irritability Subscale score adjusted for Baseline ABC Irritability Subscale score was -9.09 (SD of change of 6.76). The mean Baseline ABC Irritability Subscale score was 14.45 (SD of 8.18) and the mean study Endpoint ABC Irritability Subscale score was 5.36 (SD of 6.70).

ANCOVA analysis for two correlated samples to evaluate the mean change from Baseline to study Endpoint in the Aberrant Behavior Checklist (ABC) Irritability Subscale score adjusted for Baseline ABC Irritability Subscale score found the mean change of -9.09 to be statistically significant at $p < 0.0005$ ($F = 23.27$; $p = 0.00012$).

Subsequently, based on the clinically significant results from the Abilify® clinical trial combined with the pilot study results from the Erchonia® HLS study demonstrating the predicted effect size of the Erchonia® HLS Laser Device and associated treatment administration protocol for the proposed indication, the midpoint in the change on the ABC Irritability Subscale score is determined to be -8.5 points, and the clinically significant study success for the currently proposed full-scale clinical study is defined as a minimum mean difference of -8.5 points on the ABC Irritability Subscale score from Baseline to Endpoint between active and placebo treatment groups.

Therefore, the estimated clinically significant effect size of the Erchonia® HLS Laser Device as applied to children and adolescents with autistic disorder in the proposed clinical study based on prior experience and research is a minimum mean difference of -8.5 points on the ABC Irritability Subscale score from baseline to endpoint (week four) between active and placebo treatment groups.

SECONDARY EFFICACY OUTCOME MEASURES

The following secondary efficacy outcome measures will be evaluated in this study:

- *Positive Response Rate*: Difference in Positive Response Rate between treatment groups, where 'Positive Response Rate' is defined as satisfaction of both of the following 2 criteria:
 - ✓ $\geq 25\%$ reduction from baseline to endpoint in the Aberrant Behavior Checklist (ABC) Irritability Subscale score based on the subject's primary caregiver's rating; AND
 - ✓ Clinical Global Impressions – Improvement (CGI-I) scale rating of 1 or 2 (much improved or very much improved) at study endpoint as determined by the clinician's evaluation

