- Mean change from baseline to endpoint in the other 4 ABC Subscale scores, based on ratings by the subject's primary caregiver:
 - ✓ Lethargy/Social Withdrawal
 - ✓ Stereotypic Behavior
 - ✓ Hyperactivity/Noncompliance
 - ✓ Inappropriate Speech
- Mean change from baseline to endpoint in the global ABC score
- Change in ratings on the CGI-S from baseline to study endpoint evaluation
- Change in ratings on the CGI-I from baseline to study endpoint evaluation

STATISTICAL METHODS

Efficacy analysis will be according to the intent to treat (ITT) principle by last observation carried forward (LOCF).

Intent to Treat: Subjects will be included in the ITT analysis if they complete their baseline clinical assessments and had at least one post-randomization efficacy evaluation and corresponding baseline value.

Last observation carried forward (LOCF): Missing data will be handled by carrying forward the last observation for the relevant measure. The LOCF data set included data recorded at a given time point, or, if no observation was recorded at that time point, data carried forward from the previous time point with available data. Baseline data will not be carried forward or averaged to impute missing values for the LOCF data set.

STATISTICAL ANALYSIS

Primary Efficacy Analysis

For the continuous primary efficacy measure of ABC Irritability Subscale score, change scores will be evaluated by analysis of covariance (ANCOVA). The ANCOVA models for LOCF data sets will include the baseline measure as a covariate and treatment (active of placebo) as main effects.

Secondary Measures Analysis

- For the continuous secondary efficacy measures of the other 4 ABC Subscale scores, and the Global Score, change scores will be evaluated by analysis of covariance (ANCOVA). The ANCOVA models for LOCF data sets will include the baseline measure as a covariate and treatment (active of placebo) as main effects. A two-way significance level of 5% will be considered to be statistically significant.

- For the categorical measures of the CGI will be analyzed within the framework of the generalized Cochran-Mantel Haenszel (CMH) procedure.
- Responder rate will be evaluated using Fisher's exact test to compare the proportion of responder rates between the test and control groups.

P-values will be 2-tailed tests of significance rounded to 3 decimal places. All analyses will be performed at the 5% significance level.

SAFETY ANALYSES

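### Eight secondary comparisons are each tested at an unadjusted 5% with no link to the primary result, which leaves supporting claims, though not study success, open to false positives

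*Combined protocol and SAP*

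**What the plan says.** The section Secondary Efficacy Outcome Measures opens with "The following secondary efficacy outcome measures will be evaluated in this study" and then lists eight between-group comparisons:

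- one responder comparison ("Difference in Positive Response Rate between treatment groups");
- four subscale comparisons ("Mean change from baseline to endpoint in the other 4 ABC Subscale scores");
- one total score ("Mean change from baseline to endpoint in the global ABC score");
- CGI-S ("Change in ratings on the CGI-S from baseline to study endpoint evaluation");
- CGI-I, worded in the same way as CGI-S.

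Under Statistical Analysis, Secondary Measures Analysis, the four subscales and the global score are analysed by ANCOVA. That bullet carries the declaration rule "A two-way significance level of 5% will be considered to be statistically significant". The CGI measures go to a generalized Cochran-Mantel-Haenszel procedure and the responder rate to Fisher's exact test. Two closing sentences apply to everything: "P-values will be 2-tailed tests of significance rounded to 3 decimal places" and "All analyses will be performed at the 5% significance level".

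The supplied text contains no testing order, no condition that the primary result be significant first, no adjustment, and no label marking the secondary measures as exploratory or descriptive.

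Two other places bound the problem. The opening of the Statistical Analysis Plan makes study success depend on the primary endpoint in the ITT LOCF analysis. The Indication for Use section confines the intended claim to irritability.

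**The concern.** The plan does more than stay silent on secondary inference. For five measures it says in advance that an unadjusted 5% result counts as statistically significant, and it sets the same level for the other three. A trial that misses on irritability could therefore report a significant hyperactivity or CGI result under its own pre-specified rule. A trial that succeeds could add statements about domains the device does not affect.

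The Purpose of Study section says the data will go into a de novo application, so secondary results may be read as support. The Study Rationale speaks of reducing the severity of autistic disorder symptoms generally, as well as irritability. The pilot report already describes all five ABC subscales and the global score as significant from a series of t-tests, with no adjustment mentioned.

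A separate defect affects the family itself. CGI-I is listed as a change from baseline, but the Baseline Evaluation records CGI-S only. As written, that comparison has no baseline value.

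**Working it through.** **The plan's own figures.** The plan gives no family-wise error figure for the secondary measures, only 5% per test. Its primary sample size does reproduce. With a difference of 8.5, SD 8.9, two-sided 5% and 80% power, n = 2 × (1.96 + 0.84)² × (8.9/8.5)² ≈ 17.2, rounded up to 18 per group as stated. Nothing below changes that calculation.

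**Inputs.** Number of tests: 1 (responder) + 4 (subscales) + 1 (global) + 1 (CGI-S) + 1 (CGI-I) = 8. Level: 0.05 two-sided each. The documents give no correlations between the test statistics, so these are assumed and shown as a range.

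**Device with no effect on anything, either direction.** Under independence, 1 − 0.95⁸ = 1 − 0.663 = 33.7%. For equally correlated normal test statistics, by simulation:

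| Assumed correlation | At least one p<0.05 | At least one p<0.05 in the device's favour |
|---|---|---|
| 0 | 33.7% | 18.3% (= 1 − 0.975⁸) |
| 0.5 | 25.0% | 12.5% |
| 0.7 | about 19% | 9.6% |

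For one test alone, the corresponding figures are 5% and 2.5%.

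**Check using the structure of the measures.** A second simulation had 20 per group, the pilot SDs of change, global score as the sum of the five subscales, and response requiring both an irritability reduction and a CGI-I of 1 or 2. It used t-tests in place of ANCOVA and CMH. It also assumed a mean irritability change of −5 in both groups and a baseline of 25 for the 25% threshold. The chance of at least one p<0.05 in either direction was 29% at assumed correlation 0, 26% at 0.3, 23% at 0.5 and 18% at 0.7.

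**Two refinements to the independence figure.**

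- Fisher's exact test is conservative. At 20 per group its true size is at most about 2.5% over response rates of 5% to 95%. Then 1 − 0.95⁷ × 0.975 = 31.9%.
- If CGI-I is dropped for want of a baseline, seven tests remain: 1 − 0.95⁷ = 30.2%.

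**Effect of a gate on the primary.** If the device affects nothing, a secondary claim also requires a false-positive primary, so the chance cannot exceed 5%. It was 1.7% to 3.3% in the structural simulation. If irritability truly improves, the gate opens. The global score and the responder rate both contain irritability, so they are unlikely to be true nulls. The four other subscales, if null, carry 1 − 0.95⁴ = 18.5% under independence. With CGI-S and CGI-I also null, the figure is 1 − 0.95⁶ = 26.5%.

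**Effect of Holm.** The first step is 0.05/8 = 0.00625. With all eight null, the chance of any rejection is 1 − (1 − 0.00625)⁸ = 4.9% under independence, and 4.0% and 3.2% at correlations 0.5 and 0.7. Holm holds the family at 5% or less under any dependence.

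**The case against.** The strongest reply is that no decision in the documents depends on these tests. Success is defined on ABC Irritability alone, the indication covers irritability only, and no section proposes a claim on speech, lethargy, stereotypy, hyperactivity or CGI. One primary with labelled secondaries is already a minimal hierarchy. This stands, and it limits the point to supporting claims and reporting.

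A reader might infer that an ineffective device has a one-in-three chance of a false secondary benefit. The documents do not support that:

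- 33.7% counts results in both directions, including those where the device looks worse.
- It assumes independence, although the global score contains the subscales and the responder definition uses both ABC Irritability and CGI-I.
- It treats Fisher's test as having its full 5% size.
- It is not a ceiling either. The bound under arbitrary dependence is 8 × 5% = 40%.

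A further objection is that the declaration sentence sits in the bullet for the five continuous measures. That is correct. The CGI and responder tests are covered only by the general sentence, which sets a level without saying what will be called significant. Five tests alone would still give 1 − 0.95⁵ = 22.6% under independence.

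Finally, for a wholly ineffective device a gate alone is enough, and Holm is one choice among several. This also stands. Control within the family is needed only where irritability truly improves and other domains do not.

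**Conclusion.** The concern holds, within limits. The plan pre-specifies eight unadjusted 5% tests with no link to the primary result, and for five of them it states that 5% counts as statistically significant.

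With no device effect, the chance of at least one such result is about 19% to 25% at assumed correlations of 0.7 to 0.5, and 33.7% if the tests were independent. Counting only results in the device's favour, it is about 10% to 18% (correlation 0.7 to independence). If irritability improves and the other four subscales do not, those four carry up to 18.5%, taking independence as the upper case. All figures other than the independence values rest on assumed correlations.

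A reader might also infer that the trial's overall Type I error is inflated, or that the device could succeed through a secondary measure. It cannot: the success rule names the primary endpoint only. The matter is worth correcting because the correction is cheap, but it does not threaten the primary conclusion.

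**What to change.** In Secondary Measures Analysis, replace the two 5% sentences as they apply to the secondary measures with a rule to this effect:

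- The eight secondary comparisons are tested for significance only if the primary ANCOVA in the ITT LOCF set is significant at a two-sided 5%.
- They are then tested by Holm's procedure at a two-sided family level of 5%.
- Unadjusted p-values are reported and marked nominal. Only results that pass Holm are called statistically significant.

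An acceptable alternative is to label all secondary results descriptive and drop the significance wording for them.

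In either case, define the CGI-I comparison as the rating at study endpoint, not a change from baseline, because only CGI-S is recorded at baseline. The change should be made before unblinding.

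The cost is SAP wording only. Sample size, visits, data collection, the primary test and its power are unchanged. The downside of Holm is that the smallest of the eight p-values must be below 0.00625 for any to pass. With 18 to 20 subjects per group, some secondary results that would have been called significant will become nominal.

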Presently, the exact mechanism of LLLTT remains enigmatic, and it remains unclear the impact this technology can have on genetic aberrations. Nevertheless, preliminary studies have shown, subsequent to LLLTT, upregulation of cell bioenergetics and sequential influence on intra-cellular secondary cascades. Clinical outcomes include nerve regeneration, increased neurotransmitter release, growth factor synthesis, and neovascularization to name a few. Accordingly, auspicious positioning of laser along impaired regions of an autistic brain could elicit a positive therapeutic outcome.

SUPPORTIVE CLINICAL DATA: ERCHONIA® HLS FEASIBILITY PROOF OF CONCEPT TRIAL

BACKGROUND

In September 2012, a **feasibility proof of concept trial** based on the design - including device specifications and output, and treatment administration protocol parameters - was completed that evaluated the exact same indication proposed in this pivotal clinical trial. The feasibility proof of concept trial successfully established safety and potential effectiveness of the Erchonia® HLS Laser Device for the proposed indication for use of: "The Erchonia® HLS laser device is indicated to improve the symptoms of irritability associated with autistic disorder in children and adolescents aged five to seventeen years, inclusive."

STUDY DESIGN

The feasibility proof of concept trial was conducted as a pilot study that employed the same parameters of the currently proposed full-scale pivotal trial protocol including the Erchonia® HLS Laser Device and its output parameters, the device application with respect to the

treatment administration protocol (number, frequency and duration of treatment administrations, etc.); and the study qualification enrollment criteria.

As the study was conducted as a feasibility study, all subjects received the active device treatments with the Erchonia® HLS Laser Device.

The Aberrant Behavior Checklist (ABC) assessment tool was administered at Baseline evaluation (before receiving the first laser treatment administration) and at study Endpoint evaluation (after completion of the entire laser treatment administration protocol).

SUBJECT SAMPLE

In the feasibility study, eleven (9 male and 2 female) children and adolescents aged from 5 years 4 months to 16 years 10 months with autistic disorder who satisfied all of the study qualification criteria were enrolled.

RESULTS

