Both acupressure and acupuncture (with or without supplemental electrical stimulation administered through attachments to the handles of the acupuncture needles – Electronic Acupuncture Treatment) have been applied to specific scalp acupoints for various neurological indications including stroke, epilepsy and depression. Improvements in cognitive and behavioral functioning have been consistently reported.

STUDY RATIONALE: Considering a positive study outcome, application of the Erchonia® HLS as proposed in this pivotal trial to reduce the severity of symptoms of autistic disorder, in particular the symptoms of irritability associated with autistic disorder, in children and adolescents aged 5 through 17 years, inclusive, may provide a simple, non-invasive, safe, effective and side-effect free alternative therapy to reduce the severity of symptoms of autistic disorder in affected children and adolescents.

STUDY DESIGN

This clinical study is a double-blind, placebo-controlled randomized parallel group design.

TREATMENT GROUPS

Each subject will be randomized to the test treatment group or to the placebo treatment group, as follows:

- **Test Group:** Subjects randomized to the test group will receive the study treatments with the active (true) Erchonia® HLS device.
- **Placebo Group:** Subjects randomized to the placebo group will receive the study treatments with the 'fake' (placebo) Erchonia® HLS device.

DOUBLE BLIND DESIGN

This clinical study will be a double-blind design, such that neither the subject nor the investigator will be aware of whether a subject has been assigned to the test group or to the control group until after the study is complete.

Maintenance of study double-blind throughout the study duration will be achieved as follows:

- 1) Each subject will be randomly assigned to Treatment Group A or to Treatment Group B. Subjects assigned to Treatment Group A will be treated with the Erchonia® HLS A and subjects assigned to Treatment Group B will be treated with Erchonia® HLS B. Only the study Sponsor will know which label ('A' or 'B') corresponds to the actual (test) HLS device and which label corresponds to the 'fake' device until the final study data analysis is complete. The Sponsor will ensure that this information is stored and maintained confidentially at the Sponsor's work site. This knowledge will not be shared with the investigators, the subjects, or the study Monitor until the final data analysis is complete.

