Safety analyses will be completed on all subjects who were randomized to treatment group and received at least the first study treatment administration with the Erchonia® HLS Laser device.

Safety will be assessed by evaluating and comparing frequency and incidence of observed and/or reported adverse events between test and placebo treatment groups. A chi-square test with a continuity correction will be performed to compare the percentage of subjects who had adverse events and/or reactions between the test and placebo group subjects.

SAFETY AND CONFIDENTIALITY ISSUES

ADVERSE EVENTS

At any time throughout the study, any adverse event reported by a subject and/or subject's caregiver and/or observed by the study investigator will be recorded on the case report form and subsequently evaluated by the Principal Investigator for its relation to the study treatment and whether or not any corrective action need be taken. All applicable adverse events will be reported to the IRB.

Formal evaluation of the occurrence of any adverse events will take place at the end of each study treatment administration and each evaluation visit. In addition, subjects/caregivers will be instructed to contact the investigator at any other time that he or she believes a potential adverse event has occurred during the course of the subject's participation in the clinical study.

The investigator will record the observation or report of any adverse event and assign the relationship to the study treatment on the appropriate case report form in the subject's file and will report the occurrence to the governing IRB, if and as appropriate, within 5 days of the reported occurrence, or within 24 hours in the occurrence of a serious adverse event including death.

The only known potential adverse event associated with the use of laser devices is that long-term exposure to laser light could cause damage to eyesight. As a precaution, during all laser treatment administrations with the Erchonia® HLS at the test site, both the subject and the administration investigator will wear safety glasses that filter out the laser light spectrum. The administration investigator will wear KenTek Corporation KenTek C22-KMT-6101 light blue safety glasses and the subject will wear KenTek Corporation KGOG-6101 light blue Medium Goggles safety goggles. Additional information on this safety eyewear is contained above on pages 6-8 under the section titled: DEVICE SAFETY: RISK AND PREVENTION OF EYE INJURY.

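### The only formal safety test has little power at 20 per arm and no confidence interval is planned, so a non-significant adverse-event comparison would say little about how much harm remains possible

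*Combined protocol and SAP*

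**What the plan says.** Under SAFETY ANALYSES in the statistical analysis plan, the population is defined first: "Safety analyses will be completed on all subjects who were randomized to treatment group and received at least the first study treatment administration". With 40 children allocated equally (Subject Sample Size), that is up to 20 per arm. The comparison is then described: "Safety will be assessed by evaluating and comparing frequency and incidence of observed and/or reported adverse events between test and placebo treatment groups". One test is named: "A chi-square test with a continuity correction will be performed to compare the percentage of subjects who had adverse events and/or reactions".

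The level and sidedness come from the end of STATISTICAL ANALYSIS: "P-values will be 2-tailed tests of significance rounded to 3 decimal places", and "All analyses will be performed at the 5% significance level".

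The sample size rests on the ABC Irritability change score only (Rationale and Justification for Sample Size). Study success is likewise defined on the primary efficacy endpoint (opening of STATISTICAL ANALYSIS PLAN). Neither the safety section nor the sample-size section gives an expected adverse-event rate, a power or precision figure for safety, a confidence interval, a margin, or a rule for reading a non-significant result.

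**The concern.** A test of no difference returns a p-value. A small one suggests the arms differ. A large one does not show that they are alike, and with 20 children per arm it is the likely result even when the device causes a sizeable excess of adverse events. Without an interval, the output does not tell the reader how large an excess the data leave open.

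This matters because the sponsor intends to put the data and analysis into a de novo application for a device used in children aged 5 to 17 (PURPOSE OF STUDY). The adverse-event table will be read for reassurance. As planned, its one inferential line cannot give a quantified answer, and with no events in either arm there is no inferential line at all.

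**Working it through.** **Inputs.** From the documents: 20 per arm, continuity-corrected chi-square, two-sided 5%. The documents give no adverse-event rates, so the rates below are assumptions, shown over a range.

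**The plan's own figure.** For the efficacy endpoint, n per arm = 2(1.960 + 0.842)² × (8.9/8.5)² = 17.2, rounded up to 18, as stated. Inflation gives 18/0.89 = 20.2, which the plan takes as 20. The figure reproduces, and no safety quantity enters it.

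**Smallest result that reaches significance.** With a and b affected children per arm, n = 20, N = 40 and m = a + b, the corrected statistic is

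X² = N(|a(n − b) − b(n − a)| − N/2)² / [n² m (N − m)], compared with 3.841.

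- 5 v 0: 40 × (100 − 20)² / (400 × 5 × 35) = 256,000/70,000 = 3.66, p = 0.056, not significant.
- 6 v 0: 40 × (120 − 20)² / (400 × 6 × 34) = 400,000/81,600 = 4.90, p = 0.027, significant.
- 0 v 0: m = 0, so the denominator is zero and the test does not exist.

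With no events on placebo, six of 20 active children must be affected before the test signals.

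**What an interval would show for the same data.** The Newcombe method combines the Wilson limits of the two arms. For 5 v 0 these are 11.2% to 46.9% and 0% to 16.1%:

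- lower limit: 0.25 − √[(0.25 − 0.112)² + 0.161²] = +0.04
- upper limit: 0.25 + (0.469 − 0.25) = +0.47

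The p-value of 0.056 would be reported as no significant difference, while the interval runs from +4 to +47 points and excludes zero. For 4 v 1, p = 0.34 and the interval is −7 to +37 points.

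**Zero events.** The exact two-sided 95% upper limit for 0 of 20 is 1 − 0.025^(1/20) = 16.8%. The one-sided 95% limit is 1 − 0.05^(1/20) = 13.9%.

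**Chance of missing a fourfold excess.** The binomial probabilities of all 21 × 21 possible outcomes were summed over those with p above 0.05. A 0 v 0 result counts as a miss.

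| Assumed placebo v active rate | Planned test | Fisher exact | Uncorrected chi-square |
|---|---|---|---|
| 2.5% v 10% | 99% | 97% | 92% |
| 5% v 20% | 90% | 83% | 71% |
| 7.5% v 30% | 71% | 67% | 54% |
| 10% v 40% | 52% | 51% | 38% |
| 15% v 60% | 23% | 20% | 13% |
| 20% v 80% | 4% | 4% | 2% |

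The miss rate depends strongly on the base rate. At 5% v 20% the planned test has about 10% power.

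**The case against.** Low power for adverse events follows from sizing a 40-child trial on efficacy, and nobody would expect otherwise. The chi-square is also not the whole safety assessment. The same section plans a comparison of frequency and incidence. The ADVERSE EVENTS section has the Principal Investigator judge each event for its relation to treatment, with formal review at every treatment and evaluation visit and reporting to the IRB. A reader with the percentages and arm sizes could work out an interval. All of this stands, and it rules out saying that safety rests on the test alone. None of it puts a planned bound on the excess that remains possible.

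Three stronger readings are tempting and should not be made.

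- A reader might infer that the plan will treat p > 0.05 as proof of safety, linking the test to the STUDY RATIONALE, where a positive outcome "may provide a simple, non-invasive, safe, effective and side-effect free alternative therapy". No section says so. That sentence is conditional, sits in background text and is not tied to the adverse-event test. The ADVERSE EVENTS section itself allows for unknown risks.
- A reader might infer that any test at this size misses most fourfold excesses. The table shows otherwise: at 10% v 40% the three tests miss 52%, 51% and 38%, and at 15% v 60% all miss fewer than one in four.
- A reader might take the remark that "The feasibility proof of concept trial successfully established safety and potential effectiveness" as part of this fault. It describes a completed pilot whose results were only partly available for this review, so no judgement on it is made here.

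Some of the weakness belongs to the continuity correction itself. At 5% v 20%, dropping it raises power from 10% to 29%. That helps, but still leaves no statement of how much harm the data allow.

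**Conclusion.** The point holds in a limited form. The one formal safety analysis is a difference test with no power or precision basis at 20 per arm, and no interval or upper limit is planned. If adverse events are uncommon on placebo (5% or below, an assumption), the planned test misses a fourfold excess about 90% of the time or more. At higher base rates it does better, missing 52% at 10% v 40%. The zero-event limit and the 5 v 0 example need no assumed rate.

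The figures take 20 children per arm in the safety set, which is the planned maximum. Efficacy inference and the definition of study success are unaffected. What changes is what the trial can say about safety in children. This is a worthwhile, cheap improvement to the analysis, and corrects no contradiction in the plan.

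**What to change.** Amend SAFETY ANALYSES so that the safety summary rests on estimation:

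- Report the active-minus-placebo difference in the percentage of children with any adverse event, and separately with any device-related event, each with a 95% confidence interval. Name the method in advance (Newcombe or exact).
- Report the active-arm percentage with its exact 95% upper limit, including when no events occur. For 0 of 20, the report would say that rates up to 16.8% are not excluded.
- Keep the p-value as descriptive only.
- Add a sentence stating that a non-significant difference will not be read as evidence of safety, and that the report will give the largest excess the interval does not exclude.

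The relation of each event to treatment is already recorded on the case report form, so no new data are needed. The cost is a few sentences in the plan and a few lines of output, with no added children or visits. The real downside for the sponsor is a less favourable safety statement than an unqualified report of no significant difference.
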